4. BACKGROUND INFORMATION OF CLINICAL TRIAL

4.1. Introduction to the Condition

4.1.1. Explanation for the Condition

Primary liver cancer or HCC is the most common type of liver cancer in Asia where chronic hepatitis B virus and hepatitis C virus infections are the major causes of liver cancer. Other causes include toxic injury, typically initiated by ingestion of aflatoxin or consumption of alcohol. Incidence rates of HCC in men are more than twice those in women as men have higher rates

Confidential Page 20 of 61

of chronic hepatitis B virus (HBV) and hepatitis C virus (HCV) infection, and chronic alcohol consumption with possible hormonal influences on modulation of hepatocarcinogenesis.

HCC is the sixth most common cancer worldwide with approximately 782,000 new cases and 745,000 deaths annually.¹ and the third most common cause of death from cancer (598,000 deaths annually).² More recently in China, liver cancer is the second major cause of cancer deaths, with a mortality rate of 26.26 per 100,000 (males: 37.55 and females: 14.45 per 100,000), accounting for 19.33% of all sites of cancers. Accordingly, the estimated annual incident cases and deaths of liver cancer are 360,000 and 350,000, respectively.³

Surgical resection is the reference standard for treatment of HCC, however only a small proportion of HCC patients are candidates because of disease progression, anatomical location, and/or poor liver function. In these cases, imaging-guided percutaneous ablation can be better options. It features significant advantages including that it's minimally invasive, safe, easy to operate, easy to implement repeatedly, and has relatively low cost. Recurrence of HCC is common in patients who have undergone surgical resection; for those patients, the image-guided methods are easier and safer option than surgical resection. Indeed, image guided methods have been widely used in China.

Due to the heterogeneous epidemiology and clinical presentation of HCC worldwide, there are no universally accepted consensus practice guidelines for HCC. In Asia, there are regional and national guidelines based on the experience of the consensus group members and the practice relevant to the epidemiology. In 2011, Chinese experts published their consensus on ablation for HCC.³ In this consensus, local ablation therapy is considered as one of the radical treatments of small HCC.

Microwave Ablation to Treat HCC in China

The largest clinical experience using MW ablation to treat HCC comes from China, in part due to early adoption of MW ablation systems available only in Asia. That multicenter study of 1007 patients with primary liver cancer showed a technical success of 97.1% (1276/1363) and a local tumor progression rate of 5.9% (78/1363) with a mean follow-up time of 17.3 months (range, 3-68.9 months). The 1-, 3- and 5-year overall survival rates were 91.2%, 72.5% and 59.8%, respectively.⁵

A retrospective study of MW ablation as a first-line treatment for HCC evaluated the long-term outcomes and prognostic factors of 221 consecutive patients receiving MW ablation in Renji Hospital (Shanghai) between October 11, 2010 and December 31, 2013 were enrolled. Technique effectiveness was evaluated 1-month post-ablation. Initial complete ablation was found in 201 (90.95%) patients, secondary technique effectiveness in 8 (3.62%) patients, and the remaining 12 (5.43%) patients suffered from incomplete ablation after 2 sessions of MW ablation. No patients died within 30 days post ablation. Major complications occurred in 8 (3.8%) patients. It was concluded that MW ablation provides high technique effectiveness rate and is well tolerated in patients with HCC as a first-line treatment.

Confidential Page 21 of 61

Literature Review

Pre-clinical and clinical data has shown that MW ablation is safe and effective in liver tumors with low complication rates, high rates of technical success, lower rates of local tumor progression and promising disease-free and overall survival rates than have historically been reported for radiofrequency (RF).⁷

Based on a review of the current literature on clinical MW ablation, collectively³, the studies demonstrate that microwave (MW) ablation is a safe and effective therapy for tumors in the liver, lung, kidney and bone when compared with the current clinical standard, RF ablation. In particular, they demonstrate that MW ablation is associated with high rates of technical success, low anesthesia complication rates, low rates of local recurrence and good long-tem survival. In addition, the studies illustrate several advantages of MW ablation, including uniform cell kill within ablation zones, multiple-antenna capability, and improved perivascular ablation. The treatments were performed using multiple different MW systems characterized by different frequencies, maximum power, antenna size, antenna design, and feed line cooling mechanism. Despite differences in system design, the studies consistently established that MW ablation is safe and effective. While the majority of the studies focus on the use of microwaves for focal tumor ablation, several studies have demonstrated that microwaves are also an effective means of achieving precoagulation during liver resections.

4.1.2. Therapeutic Option and Prognosis

Microwave Ablation Compared with Hepatic Resection

Shibata et al ⁸ conducted a randomized trial of patients with multiple resectable liver metastases from colorectal cancer who underwent either intraoperative MW ablation (14 patients) or hepatectomy (16 patients). There was no significant difference in survival rates between the two groups. The 1-, 2-, and 3-year survival rates and mean survival times were 71%, 57%, 14%, and 27 months, respectively, in the MW group, and 69%, 56%, 23%, and 25 months, respectively, in the hepatectomy group. However, operative blood loss and the need for transfusions were significantly lower in the MW ablation group. Recently, Zhang et al ⁹ compared the efficacy of liver resection with percutaneous MW ablation for patients with single small (<3 cm) HCCs. Patients (n=190) had Child Pugh A cirrhosis. Major complications were significantly higher in the resection group (22.1% vs 5.9%, p=0.004). There was no significant difference in overall survival, but the disease-free survival was significantly higher in patients who underwent resection, except for patients with portal hypertension (overall survival [OS] and disease-free survival [DFS] were similar between groups).

Shi et al 10 compared MW ablation and surgical resection for treating patients with HCC within Milan criteria. For solitary tumors ≤ 3 cm, DFS and OS were similar for patients treated with MW ablation and resection. For all patients within Milan criteria, there was no difference in OS, but resection was associated with a higher rate of DFS. Chong et al 11 conducted a retrospective study comparing MW ablation with liver resection and found that with propensity score matching of the two groups that resulted in 63 matched pairs, liver resection had better overall survival and disease-free survival in patients with albumin-bilirubin grade 1. However,

Confidential Page 22 of 61

MW ablation showed a significantly better overall survival and a trend towards better disease-free survival in patients with albumin-bilirubin grade 2 or 3.

Adoption of MW ablation systems has previously been limited by technical problems associated with suboptimal power handling, large antenna diameter, antenna shaft heating and unpredictable heating patterns. Despite these limitations, the results of clinical MW ablation studies have historically compared favorably with those of RF ablation. In a recent meta-analysis, RF ablation and MW ablation had similar 1- to 5-year overall survival, disease-free survival, local recurrence rate, and adverse events (AEs). However, MW ablation demonstrated a superior 6-year overall survival. As MW ablation technology has advanced, and our understanding of MW energy delivery has improved, MW ablation systems have become increasingly utilized in interventional oncology practices.

4.2. Application of Investigational Product

Thermal ablation is increasingly utilized in the treatment of primary and metastatic liver tumors, both as curative therapy and as a bridge to transplantation. Recent advances in high-powered MW ablation systems have allowed physicians to realize the theoretical heating advantages of MW energy compared with other ablation modalities. As a result, there is a growing body of literature detailing the effects of MW energy on tissue heating, as well as its effect on clinical outcomes.¹³

Multiple-Antenna Microwave Ablation

Several reports have demonstrated that multiple-antenna MW ablation is safe and improves treatment efficacy. Multiple antennas were used in the studies by Simon et al¹⁴ and Meredith et al¹⁵ described above. In addition, Yu et al¹⁶ treated nine patients with intraoperative MW prior to resection of HCC. The ablations were performed with a single straight antenna, three straight antennas, or three looped antennas. The coagulation volumes were significantly larger for the three-antenna configurations and the study showed that multiple antennas are a promising way to safely, rapidly and effectively treat large HCCs. Uniform cell kill within the ablation zone was also seen in this study.

Microwave Ablation with a Gas-Cooled System

The results of HCC treatment with a high-power, gas-cooled, multiple antenna-capable MW device were retrospectively reviewed by Ziemlewicz et al. ¹⁷ A total of 107 HCCs in 75 patients were treated via percutaneous approach. All procedures were performed with a single MW system (Certus) with one to three 17-gauge antennas. Primary technique effectiveness rate was 91.6% (98 of 107) overall. Ziemlewicz concluded that treating HCC with a gas-cooled, multiantenna-capable MW ablation device is safe, with promising treatment effectiveness.

4.3. Product Registration and Reason for Clinical Trial Registration in China

The Certus Microwave Ablation System and Accessories have been cleared by the United States (US) Food and Drug Administration (FDA) and has been in clinical use since 2011 in the United States. The most common applications by clinicians have been the ablation of liver, kidney, and lung tumors. Additional, but less common uses have been nerve ablation and the Confidential

Page 23 of 61

ablation of soft tissue tumors in bone.

This device has not been used in general ablation procedures in the Chinese population. Therefore, the clinical study is designed to support the registration of the device in China.

5. FEATURES, STRUCTURAL COMPOSITION, OPERATION PRINCIPLE, MECHANISM OF ACTION, AND STUDY POPULATION

5.1. Features

5.1.1. Design Features of Study Product

Neuwave Medical's Certus Microwave Ablation System and Accessories consists of Software version 3.0.X and the accessories NEUWAVE Certus PR, NEUWAVE Certus LK, and NEUWAVE Certus SR ablation probes. Several accessories designed to allow for the mechanical interfacing of the Power Distribution Module (PDM) to a variety of vendors' CT (computed tomography) tables are also available. These accessories are ease-of-use and convenience accessories that do not impact the clinical functionality of the system and thus are not described in detail.

The Certus system uses a CO₂ cooling system where all other MW systems use sterile water, but the risks associated with this cooling system do not differ from the risks inherent in cryogenic ablation systems, also widely accepted in clinical use. Thus, The Certus system does not introduce new hazards or intended uses.

The Certus Microwave Ablation System and Accessories are intended to ablate/coagulate soft tissue using microwaves in the United States. The Certus Microwave Ablation System and Accessories are general purpose thermal ablation tools used by physicians to ablate softtissue tumors in a wide variety of tissue and disease states in the United States.

The risk/benefit profile of the Certus Microwave Ablation System and Accessories is acceptable for the intended use of the ablation/coagulation of soft tissue relative to other medical alternatives.

5.2. Study Population

The study population will include 137 Chinese patients with a single HCC tumor up to 5 cm or a maximum of 3 HCC tumors up to 3 cm per tumor.

6. INDICATIONS AND CONTRAINDICATIONS, PRECAUTIONS

6.1. Indications

The Certus Microwave Ablation System and Accessories form a Microwave Ablation System, which is intended to ablate/coagulate soft tissue. The Certus Microwave Ablation System and Accessories are general purpose thermal ablation tools used by physicians to ablate soft tissue

Confidential Page 24 of 61

tumors in a wide variety of tissue and disease states. The most common applications by clinicians have been the ablation of liver, kidney and lung tumors. Additional, but less common uses have been the ablation of soft tissue tumors in bone and nerve ablation.

6.2. Contraindications

The Certus Microwave Ablation System and Accessories is contraindicated for:

- Use in cardiac procedures.
- Pregnant patients potential risks to patient and/or fetus have not been established.
- Patients with implantable pacemakers or other electronic implants. Implanted electronic devices may be adversely affected by MW power.
- Use on the central nervous system.
- Endometrial applications.

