	Visit 1	Visit 2A	Visit 2B	Visit 3	Visit 4	Visit 5	Visit 6	Visit 7	Visit 8	Visit 9	Visit 10	Visit 11	
Interval Windows: Activities	within 14 d prior to	Day 0	within 7 d after	1 month (+/- 7 d)	3 months (+/- 7 d)	6 months (+/-14 d)	9 months (+/-14 d)	12 months (+/-14 d)	6 months 9 months 12 months 18 months 24 months 30 months (+/-14 d) (+/-14 d) (+/-28 d) (+/-28 d)	24 months. (+/-28 d)		36 months (+/-28 d)	Ψ/Z
	2		2										
Length of hospital stay			×										
Complete tumor ablation			×	×									
evaluation													
LTP evaluation ⁸				×	×	×	×	×	×	×	×	×	
Progression-free survival ⁸				×	×	×	×	×	×	×	×	×	
Concomitant meds ⁹	×	×	×	×	×	×	×	×	×	×	×	×	×
Concomitant procedures ¹⁰			×	×	×	×	×	×	×	×	×	×	×
AEs and SAEs ¹¹		X	×	×	×	×	×	×	×	×	×	×	×

Symbol: "O" means that ultrasound and computed tomography (CT) scans are optional for Screening.

Cooperative Oncology Group; EORTC QLQ = European Organization for Research and Treatment of Cancer Quality of Life Questionnaire; HCC = hepatocellular Abbreviations: ab. = ablation; AEs = adverse events; ASA = American Society of Anesthesiologists; CT = computed tomography; d = days; ECOG = Eastern carcinoma; LTP = local tumor progression; meds = medications; MRI = Magnetic Resonance Imaging; NPRS = numeric pain rating scale; rad = radiation; SAEs = serious adverse events; SOC = standard of care; surg = surgical; USV = unscheduled visit.

Notes:

- 1. Review and collect medical, surgical, and radiation histories, including alcohol consumption and hepatitis, if applicable. Note: HCC diagnosis does not need to be reported as medical history.
- At minimum, an MRI of the liver must be taken at Baseline/Screening (per each study site's SOC) to ascertain tumor type, location, and size (measured in longest diameter and the diameter that is perpendicular to this longest diameter). Tumor size must be measured with at least 2D imaging. The MRI must ς.

be taken within 14 days prior to ablation (Visit 2A). Ultrasound and/or CT are optional.

- 3. An MRI must be taken within 7 days following the ablation procedure.
- Ultrasound and/or CT will be used to guide the probe into place and confirm accurate placement of the probe prior to ablation . For ultrasound, a video of the ablation may be submitted to the Sponsor. 4.
- Serum pregnancy test, for women of childbearing potential only, must be performed within 14 days prior to ablation (Visit 2A); otherwise the test must be repeated and available prior to ablation. 5

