7.1.5. Selection of Patients

1) Inclusion criteria

- Diagnosed primary or recurrent HCC determined in accordance with the institution's SOC procedure, single tumor size up to 5 cm or a maximum of 3 tumors up to 3 cm per tumor. Tumor size must be measured with at least 2-dimensional (2D) imaging.
- Scheduled for MW ablation of the liver.
- Performance status 0-2 (Eastern Cooperative Oncology Group classification).
- Functional hepatic reserve based on the Child-Pugh score (Class A or B).
- Give voluntary, written informed consent to participate in this study and willing to comply with the study-related evaluation and procedure schedule.
- At least 18 years of age.

2) Exclusion criteria

- ASA score ≥ 4.
- Active bacterial or fungal infections which are clinically significantly.
- Chemotherapy or radiation therapy for HCC performed within 30 days prior to the study procedure.
- Patient with implantable pacemakers or other electronic implants.
- Planned/ scheduled liver surgery.
- Platelet count ≤ 50 × 10⁹/L.
- Patients with uncorrectable coagulopathy at time of screening based on investigator judgement. Severe blood coagulation dysfunction (bleeding tendency, prothrombin time [PT] was greater than normal control for 3~5 seconds, platelet count [PLT] was less than 50x10⁹/L, and the international normalized ratio (INR) was greater than 1.5).
- Patient with renal failure and on renal dialysis.
- Scheduled concurrent procedure other than MW ablation in the liver.
- Pregnant or breast feeding.
- Physical or psychological condition which would impair study participation.
- Participation in any other interventional clinical study within 1 month before screening and concurrently during the study.
- The patient is judged unsuitable for study participation by the investigator for any other reason.

3) Criteria of Sponsor's Discontinuation of the Trial

The Sponsor has the right to terminate the study early for a single site, multiple sites or all sites temporarily or permanently. Reasons may include, but are not limited to: safety issue or ethical issue, inaccurate or incomplete data record, non-compliance or dissatisfactory quality or quantity of the recruited patients. Health authorities also have the right to terminate a study.

Confidential Page 28 of 61

This study does not require a Data Safety Monitoring Board.

Other criteria:

Patients may be withdrawn if any of the following complications or adverse situations occur:

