Microwave ablation (using the Certus Microwave Ablation System only) may be performed for recurrence of target tumor(s) or to achieve complete tumor ablation with adequate margin (A0) of the target tumor(s) if the initial ablation had an insufficient margin, if the treating physician deems appropriate and necessary. While repeat ablations for a recurrence may be conducted at any point during the study duration, repeat ablations to correct an ablative margin may only be performed within the first 30 days of the original ablation (by Visit 3).

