 - o Renal function tests (Urea, creatinine, and electrolytes [sodium, potassium, and chloride]).
 - Complete blood count (differential cell count and platelet count).
 - o Alpha-fetoprotein test.
 - o Serum pregnancy test, for women of childbearing potential only.
- ECOG performance status.
- Child-Pugh score.
- ASA score.
- Include all relevant medications taken within 14 days prior to the ablation (Visit 2A).
 Relevant medications include chemotherapy, blood-thinning or coagulation, NSAIDs, those medications used to treat AEs, and those used for hepatitis (if concurrently treating).

Visit 2 - Ablation Through Discharge

The ablation procedure (Visit 2A), followed by post ablation observation and discharge (Visit 2B).

Visit 2A—Day of Ablation

Confirm inclusion and exclusion criteria prior to performing the activities below and collecting the respective data:

Ultrasound and/or CT scan to guide the probe to the tumor and confirm accurate
placement of the probe prior to emitting the microwaves. For ultrasound, a video of the
ablation may be submitted to the Sponsor. The ultrasound videos will be used to review
microbubble formation to see if there is a correlation with ablation area.

Confidential Page 37 of 61

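### The protocol requires a pregnancy test within 14 days before the original ablation but states none before a repeat ablation with the same contraindicated device

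*Protocol*

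**What the plan says.** Section 6.2 of the protocol lists pregnancy among the contraindications of the system: "Pregnant patients potential risks to patient and/or fetus have not been established". It also lists electronic implants: "Patients with implantable pacemakers or other electronic implants. Implanted electronic devices may be adversely affected by MW power". Neither entry is tied to a particular procedure or visit. Section 7.1.5 separately makes pregnancy an entry exclusion ("Pregnant or breast feeding").

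The testing rule is in Table 1 note 5: "Serum pregnancy test, for women of childbearing potential only, must be performed within 14 days prior to ablation (Visit 2A"). The note adds that a test outside that window must be repeated, with the result available before ablation. Table 1 marks the test at screening only, and Section 7.2.4 lists it under Visit 1 only. At Visit 2A the site must re-check eligibility: "Confirm inclusion and exclusion criteria prior to performing the activities below". No later visit carries that instruction.

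Section 7.2.2 allows re-treatment with the Certus system only. For recurrence: "While repeat ablations for a recurrence may be conducted at any point during the study duration". For margins: "repeat ablations to correct an ablative margin may only be performed within the first 30 days of the original ablation (by Visit 3"). Follow-up lasts 36 months.

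The laboratory lists for Visit 2B and Visits 3 to 11 contain coagulation, liver, renal, blood count and AFP tests. The unscheduled-visit list contains no laboratory tests. SAP 8.3.1 reports the pregnancy test result as a baseline characteristic, and SAP 8.5.3 names serum HCG among the laboratory variables.

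**The concern.** A contraindication attaches to the device and so applies each time it is used. The protocol evidently did not think the physician's awareness was enough at first use, because it requires a serum test there and sets a 14-day limit on its age. A duty not to treat a pregnant patient does not by itself reveal a pregnancy that nobody has recognised.

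Elsewhere the protocol plans for re-ablation. Adverse-event collection runs for 30 days after any ablation, original or additional (Section 7.1.7), and procedure details are to be collected for re-ablations (Table 1 note 7). The pregnancy check was not carried forward in the same way, and no reason is given. That looks like an omission rather than a decision.

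At stake is a rare but severe and avoidable exposure. Section 14.2 counts fetal distress, fetal death and birth defects among the serious adverse events. The concern is patient safety only and does not touch estimation.

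**Working it through.** The plan states no maximum age for a pregnancy test at a repeat ablation, so there is no such figure to reproduce. The benchmark is its own limit of 14 days at the original ablation.

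**Inputs**
- Required test: 0 to 14 days before the original ablation (Table 1 note 5).
- Margin correction: up to day 30 (Section 7.2.2).
- Recurrence: any time in a 36-month follow-up (Section 7.2.2; Synopsis, study duration).
- Conversion: 1 month = 30.4375 days (SAP 8.1.7).

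**Formula.** Age of the last required test = days since the original ablation + 0 to 14 days.

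| Repeat ablation | Calculation | Age of last required test (days) |
|---|---|---|
| Margin correction, latest | 30 + 14 | up to 44 |
| Recurrence, month 3 | 3 × 30.4375 = 91.3; + 14 = 105.3 | 91 to 105 |
| Recurrence, month 12 | 12 × 30.4375 = 365.25; + 14 = 379.25 | 365 to 379 |
| Recurrence, month 24 | 24 × 30.4375 = 730.5; + 14 = 744.5 | 731 to 745 |
| Recurrence, month 36 | 36 × 30.4375 = 1,095.75; + 14 = 1,109.75 | 1,096 to 1,110 |

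A margin correction done soon after the original ablation can still fall inside 14 days. From month 3 on, no required test can: the smallest age there is already 91.3 / 14 = 6.5 times the limit. These ages describe how stale the test is; they do not measure risk.

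**Could a later test be required elsewhere?**
- Scheduled visits after ablation: Visit 2B and Visits 3 to 11, ten in all. Pregnancy tests scheduled: 0 of 10.
- Note 5 speaks of ablation, but its parenthesis names Visit 2A, which limits it to the original procedure.
- SAP 8.3.1 treats the result as a baseline item. SAP 8.5.3 lists HCG as a variable to summarise. An analysis plan does not order a test, and the protocol schedules none after screening.

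**How many women?** This cannot be computed. The documents give neither the number of women of childbearing potential expected among the 137 patients nor the share of patients who will be re-ablated. The literature progression rate in Section 4.1.1 is per tumor, over a mean of 17.3 months, and from another study. Turning it into a count would need several further assumptions with no source here.

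**The case against.** The strongest reply is that treating a pregnant patient would breach the plan, not follow it. Section 6.2 is unqualified, Section 13.1 requires use according to the protocol and the instructions for use, Section 6.3 restricts use to trained staff, and Section 7.2.2 allows a repeat ablation only if the physician finds it appropriate and necessary. This stands. A reader might infer that the protocol permits re-treatment of a pregnant woman, and the documents do not support that. The gap is in verification.

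The second reply is that the check may exist in material not seen here. Section 6.3 points to accompanying documents for the full warnings, Section 13.3.2 makes the consent form a separate attachment, and the case report form pages were not available. This also stands. The claim is limited to the available text; if one of those documents requires a test before each use, a cross-reference closes the point.

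Third, a reader might extend the point to electronic implants and infer that one placed during follow-up would go unnoticed. That goes too far. Relevant concomitant procedures are collected at Visit 2B, at every follow-up visit and at unscheduled visits, and in-patient hospitalisation is generally reportable as a serious adverse event to the end of the study. An implant would often reach the study record. That is not a confirmation before the procedure, but it makes the implant check secondary.

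Finally, the numbers are small and the expected harm smaller, since it would also require a pregnancy that nobody had recognised. This is conceded, and it limits the severity.

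**Conclusion.** The point holds as a missing verification step. In the available text, the 14-day pregnancy test required before the original ablation is not required before a repeat ablation with the same device. The last required test can then be up to 44 days old at a margin correction and about 1,110 days old at a recurrence treated at month 36.

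This rests on reading Section 6.2 as applying at every use, which its unqualified wording supports, and on reading note 5 as limited to the original procedure, which its reference to Visit 2A supports. It is subject to the instructions for use, consent form and case report form, which could not be checked.

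The long intervals might suggest a substantial hazard. The documents do not support that: the number of women affected is likely to be very small and cannot be derived. The case for change is that the possible harm is severe and the check is simple. It is a cheap patient-safety improvement of minor severity, with no effect on any endpoint, the sample size or any analysis.

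**What to change.** Amend Table 1 note 5 and Sections 7.2.2 and 7.2.4 so that the serum pregnancy test within 14 days, for women of childbearing potential, applies before any ablation procedure, original or additional. A positive result would bar use of the device, as Section 6.2 already does. Add one item to the re-ablation page confirming that no Section 6.2 contraindication is present; this covers implants as well. The other entry criteria need not be re-applied.

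Before amending, the sponsor should see whether the instructions for use, consent form or re-ablation page already requires this. If so, a cross-reference in note 5 is enough.

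The cost is a protocol amendment, one case report form item for each re-ablated patient, and a blood test for a very small number of women. Childbearing potential is already among the baseline characteristics to be reported (SAP 8.3.1), so the women concerned should be identifiable. The amendment is more than a wording change in process terms: because it concerns patient safety, it may count as major under Section 15 and need ethics committee approval, and regulatory approval if required, before it takes effect at the four sites. It could be included in the next planned amendment.
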